3.2.1. Regimens

3.2.1.1. Episodic Regimen

The individual dose of rFIXFc to treat bleeding episodes will be based on the subject's clinical condition, type and severity of the bleeding event, and if indicated, FIX levels. A subject's PK profile and dosing levels from the parent study may also be used to guide dosing decisions. Subjects <12 years of age entering from another rFIXFc study will not be offered this option, but can opt to receive an episodic regimen once they reach the age of 12 years during the study.

3.2.1.2. Prophylaxis Regimens

The Investigator may consider the following options for prophylaxis to target a FIX trough of up to 5%, but is encouraged to use the lowest effective dose targeting a FIX trough level between 1% and 3%. If bleeding episodes occur at FIX trough levels of 1% to 3%, further adjustments to dose or interval over the course of the study will target trough levels of up to 5%. In pediatric subjects <12 years of age, doses may be adjusted up to a maximum prophylactic dose of 100 IU/kg, with the interval decreased to twice a week, if necessary to maintain adequate FIX activity trough levels and prevent spontaneous bleeding events.

Details for each dosing option, including, if applicable, the date of change, new dose and/or dosing interval, and reason(s) for the regimen change will be recorded on the appropriate eCRF each time a change is made.

Option 1: Weekly Prophylaxis

Dosing is approximately 20 IU/kg to 100 IU/kg every 7 days. The dose should be based on the subject's clinical profile observed in the parent rFIXFc study and his individual pharmacokinetic (PK) profile, trough, and/or peak (recovery) values.

Option 2: Individualized Prophylaxis

Dosing is approximately 100 IU/kg every 8 to 16 days, or 2 times per month. The dosing interval should be based on the subject's clinical profile observed in the parent rFIXFc study, and his individual PK profile, trough, and/or peak (recovery) values.

Option 3: Personalized Prophylaxis

If optimal prophylaxis dosing cannot be achieved using either of the above options, the Investigator may further personalize dosing to meet the needs of individual subjects.

The Investigator may consider the following personalized dosing options:

- Addition of "prevention" doses prior to strenuous activity
- Targeting a FIX trough level of >5%, if warranted by the bleeding history and/or activity level
- Dosing 2 times per week, e.g. 25 IU/kg, twice weekly, versus 50 IU/kg, once weekly, for subjects who may have better control with such a regimen. For pediatric subjects <12 years of age, the dose may be adjusted up to 100 IU/kg twice weekly.

The Investigator is not limited to the options above, and should consult the Medical Monitor for further consideration of a subject's dosing options. The personalized prophylaxis dosing option will require consultation with the Medical Monitor.

3.2.2. Surgery and Rehabilitation

If a subject requires emergent or elective surgery while participating in this study, he may be treated with the dose and regimen of rFIXFc deemed appropriate for the type of surgery. If a subject had a major surgery before the implementation of Protocol Amendment 2 of 9HB01EXT, only major surgeries that were not prescheduled were to be reported as SAEs. However, for subjects having a major surgery after the implementation of Protocol Amendment 2, all major surgeries were to be reported as SAEs.

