15.1.3. Serious Adverse Event

An SAE is any untoward medical occurrence that, at any dose:

- results in death
- in the view of the Investigator, places the subject at immediate risk of death (a life-threatening event); however, this does not include an event that, had it occurred in a more severe form, might have caused death
- requires inpatient hospitalization or prolongation of existing hospitalization
- results in persistent or significant disability/incapacity
- results in a congenital anomaly/birth defect

CONFIDENTIAL

The information contained herein may not be used, disclosed, or published without the written consent of Biogen Idec MA Inc.

All major surgeries will be reported as SAEs. An SAE may also be any other medically important event that, in the opinion of the Investigator, may jeopardize the subject or may require intervention to prevent one of the other outcomes listed in the definition above. (Examples of such medical events include allergic bronchospasm requiring intensive treatment in an emergency room or convulsions occurring at home that do not require an inpatient hospitalization).

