8.2. Adverse Events

AEs will be classified using the Medical Dictionary for Regulatory Activities (MedDRA) system organ classes and preferred terms. MedDRA version 15.0 will be used throughout the study. All AEs will be listed.

In general, AEs will be analyzed based on *incidence*, defined as the proportion of subjects who had at least one occurrence of an event out of the number of subjects in the Safety Analysis Set.

All AE listings will include the onset and resolution study days relative to 9HB01EXT Study Day 1. AEs that are emergent during a major surgical/rehabilitation period, AEs that are emergent on the day of surgery, and AEs that occur during the gap of greater than 14 or 7 days will be flagged. In addition, a separate listing will be provided for AEs that are emergent during a major surgical/rehabilitation period.

AEs occurring during a major surgical/rehabilitation period with an onset date on the day the surgical/rehabilitation period starts or on the day of the surgery will be included in the summaries of the study AEs but excluded from the summaries or listings of AEs occurring during a major surgical/rehabilitation period. Consideration is given to AEs with an onset date at the start of the surgical/rehabilitation period in the event the pre-surgical dose was administered the day before the surgery.

Events of overdose will not be included in the AE summary tables unless they are reported as AEs.

The algorithm for the determination of AEs that are emergent during a major surgical/rehabilitation period, AEs with an onset date on the day of the surgical/rehabilitation period starts or on the day of the surgery, and AEs that are emergent during a treatment regimen period when an onset date is partially or completely missing is described below.

- If the onset date of an AE is present, then the date of onset will be compared with the start/stop dates of the major surgical/rehabilitation period and treatment regimen period to determine whether the AE is during a major surgical/rehabilitation period, on the day of the surgical/rehabilitation period starts, on the day of the surgery, or during a treatment

regimen period. If the onset of the AE is on the day of the treatment regimen change, then it will be attributed to the previous treatment regimen.

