8.2.2. Treatment-emergent Adverse Events

In general, an AE will be regarded as treatment-emergent if it was present prior to receiving the first injection of rFIXFc in the parent study and subsequently worsened in severity, or was not present prior to receiving the first injection but subsequently appeared before the subject's last visit on study or the follow-up phone call, whichever came later (or the date of withdrawal/loss to follow-up).

All AEs that occurred on or after 9HB01EXT Study Day 1 will be considered treatment-emergent in study 9HB01EXT. AEs that were treatment-emergent in the parent studies and carried over to study 9HB01EXT without worsening in severity will be considered the same AEs and will not be counted again in study 9HB01EXT.

The incidence of TEAEs will be summarized by system organ class (SOC) and preferred term. Unless specified otherwise, SOCs and preferred terms within each SOC will be presented alphabetically. For the purpose of summarization, a subject is counted once in a SOC or preferred term if the subject reported one or more events in that SOC or preferred term. Unless specified otherwise, percentages will be based on the number of subjects in the Safety Analysis Set.

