8.2.6. Serious Adverse Events

Any AE reported as resulting in death, immediate risk of death (life threatening), inpatient hospitalization or prolongation of existing hospitalization, persistent or significant disability/incapacity, or a congenital/anomaly/birth defect will be classified as an SAE by the Investigator. An SAE may also be any other medically important event that, in the opinion of

the Investigator, may jeopardize the subject or may require intervention to prevent one of the other outcomes listed above.

All SAEs will be listed; treatment-emergent SAEs will be summarized by SOC and preferred term.

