Summary of prophylactic compliance
Summary of EPD entry compliance
Overall summary of rFIXFc treatment-emergent adverse events
Summary of rFIXFc treatment-emergent adverse events by preferred term in descending order of incidence
Summary of rFIXFc treatment-emergent adverse events by severity
Summary of severe rFIXFc treatment-emergent adverse events by preferred term in descending order of incidence
Summary of rFIXFc treatment-emergent adverse events by relationship to treatment
Summary of rFIXFc treatment-emergent serious adverse events
Summary of anti-rFIXFc antibodies
Surgery subgroup – Summary of Investigators'/Surgeons' assessment of subjects' hemostatic response to rFIXFc post major surgery
Surgery subgroup – Number of injections and dose required to maintain hemostasis during major surgery
Surgery subgroup - Estimated total blood loss during major surgery
Surgery subgroup – Total rFIXFc consumption (IU/kg) per major surgery
Surgery subgroup - Summary of number of bleeds after surgery per major surgery
Summary of Investigators'/Surgeons' assessment of subjects' hemostatic response to rFIXFc post minor surgery
Number of injections and dose required to maintain hemostasis during minor surgery
Estimated total blood loss during minor surgery
Total rFIXFc consumption (IU/kg) per minor surgery
Summary of number of bleeds after surgery per minor surgery
Summary of laboratory results and change from study 9HB01EXT baseline: Hematology
Shifts from study 9HB01EXT baseline to minimum/maximum post-baseline value for laboratory results: Hematology
Summary shifts from study 9HB01EXT baseline to minimum/maximum post-baseline value for laboratory results: Hematology
Summary of potentially clinically significant laboratory abnormalities: Hematology
Summary of laboratory results and change from study 9HB01EXT baseline: Blood Chemistry from study 9HB01EXT baseline to minimum/maximum post-baseline value for laboratory results: Blood Chemistry
Summary of shifts from study 9HB01EXT baseline to minimum/maximum post-baseline value for laboratory results: Blood Chemistry
Summary of potentially clinically significant laboratory abnormalities: Blood Chemistry
Summary of vital sign results and change from study 9HB01EXT baseline
Summary of clinical abnormalities from study 9HB01EXT baseline in vital signs

List of Listings (Listing titles are suggested. If appropriate, listing titles may change during their creation.)

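### The SAE tables pool two reporting rules for prescheduled major surgery, divided at Protocol Amendment 2, and no planned output applies one rule throughout

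*SAP*

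**What the plan says.** SAP 3.2.2 describes two rules for the same data set. Before Protocol Amendment 2, "only major surgeries that were not prescheduled were to be reported as SAEs". After it, "for subjects having a major surgery after the implementation of Protocol Amendment 2, all major surgeries were to be reported as SAEs". The current protocol carries only the later rule: "All major surgeries will be reported as SAEs" (Protocol 15.1.3).

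For analysis, SAP 8.2.1 plans an overall summary that includes subjects with a treatment-emergent SAE. SAP 8.2.6 adds: "All SAEs will be listed; treatment-emergent SAEs will be summarized by SOC and preferred term". The SAP's list of tables has one matching entry, "Summary of rFIXFc treatment-emergent serious adverse events". SAP 8 gives safety results by parent study and in total.

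Two provisions decide where a surgery SAE is counted.

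- SAP 8.2.1 places AEs from major surgical/rehabilitation periods in the surgery subgroup column of the overall summary and keeps them out of the other AE tables.
- SAP 8.2 makes an exception. AEs with onset on the day of surgery, or on the day the surgical period starts, "will be included in the summaries of the study AEs but excluded from the summaries or listings" of surgical-period AEs.

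**The concern.** Long-term safety is the primary objective, and SAE incidence is one of its main summaries. A prescheduled major operation is an SAE or not depending on which side of an amendment it falls, with nothing clinical to tell the two apart. The SAP records the change openly, but no planned table or sensitivity analysis takes account of it. The re-runs in SAP 9 cover disposition, exposure, bleeding, response and dosing outputs, not adverse events. SAP 8.2.6 restates the usual seriousness criteria without mentioning the surgery rule, so a reader of the SAE table would not learn from that section that planned operations are in part of the data and absent from the rest.

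**Working it through.** The plan states no SAE rate, so there is no figure to reproduce. The check traces a surgery SAE through the SAP and then sizes its effect.

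**Routing**

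1. Treatment emergence: "All AEs that occurred on or after 9HB01EXT Study Day 1 will be considered treatment-emergent in study 9HB01EXT" (SAP 8.2.2). A major surgery reported as an SAE during the extension qualifies.
2. Onset on the day of surgery or the first day of the surgical period: under the SAP 8.2 exception the event enters the study AE summaries, and so the SAE table of SAP 8.2.6.
3. Onset later in the surgical period: under SAP 8.2.1 the event appears only in the surgery subgroup column of the overall summary. The two rules are pooled there as well.
4. Surgery that was not prescheduled: an SAE under both rules, so the date makes no difference.
5. Prescheduled surgery: reportable after Amendment 2, not reportable before it.

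**Size**

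Incidence is "the proportion of subjects who had at least one occurrence of an event out of the number of subjects in the Safety Analysis Set" (SAP 8.2). Let k be the number of subjects whose only SAE is a prescheduled major surgery after Amendment 2, and N the number in the Safety Analysis Set. The shift in overall incidence is k/N. The same surgeries before the amendment would add 0/N = 0.

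The planned sizes are 100 from 998HB102 and 20 from 9HB02PED (SAP 3.3.1), and 100 + 20 = 120, which agrees with the protocol's approximate total. The value of k is not in the documents and is assumed.

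| Group | k | k/N | Shift (percentage points) |
|---|---|---|---|
| Overall | 1 | 1/120 | 0.8 |
| Overall | 2 | 2/120 | 1.7 |
| Overall | 5 | 5/120 | 4.2 |
| From 998HB102 | 1 | 1/100 | 1.0 |
| From 9HB02PED | 1 | 1/20 | 5.0 |

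As an illustration, suppose that 20 subjects have some other SAE and 5 have only a prescheduled major surgery. If all 5 operations precede Amendment 2, incidence is 20/120 = 16.7%. If all 5 follow it, incidence is 25/120 = 20.8%. The clinical facts are the same in both cases.

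A subject who already has another SAE does not change overall incidence. He can still change an SOC or preferred-term row, because the surgery may be coded to a row he would not otherwise be in.

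**The case against.** The case on the other side is substantial, and most of it stands as a limit on the point.

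- **Disclosure.** The rule change is stated openly in SAP 3.2.2, and the listings help. SAP 8.2 flags day-of-surgery and surgical-period AEs, and all SAEs are listed. This stands, but the flags show neither whether a surgery was prescheduled nor which rule applied, and they do not alter the tables.
- **Routing.** SAP 8.2.1 keeps surgical-period AEs out of most AE tables, so it would be wrong to infer that every major-surgery SAE reaches the SOC/preferred-term table. That depends on the recorded onset date. The 8.2 exception nevertheless admits an event dated to the operation, and events dated later are still pooled in the overall summary.
- **Size.** SAP 7.6 describes the surgery subgroup as small, and that subgroup also holds unplanned surgeries, pre-amendment surgeries and subjects with other SAEs. A reader might infer a shift of ten points or more. That would need at least 12 of 120 subjects with a prescheduled post-amendment operation and no other SAE, and nothing in the documents supports such a number.
- **Consequence.** All analyses are descriptive (Protocol 16), no SAE table is planned by calendar period or amendment, and the primary endpoint, inhibitor development, is untouched. A reader might infer that a planned comparison of early with late study time is biased. No such comparison is planned. What is affected is the meaning of the pooled SAE percentage.
- **Seriousness.** It is tempting to call these events serious by administrative rule alone. Inpatient hospitalization is itself a seriousness criterion (Protocol 15.1.3), and many planned major operations would meet it. This bears on how the flag should be defined.

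**Conclusion.** The point holds in a limited form. SAEs were collected under two definitions, and both SAE outputs pool them, so a prescheduled major surgery contributes to SAE incidence after Amendment 2 and not before. Overall incidence changes by 0.8 points for each subject with no other SAE (1.0 or 5.0 within the parent-study groups). Over an assumed 1 to 5 such subjects the overall shift is 0.8 to 4.2 points. SOC and preferred-term rows can change whether or not the subject has another SAE.

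These figures rest on planned rather than actual sample sizes, on an assumed count, and on surgery SAEs being reported as the rule in force required. With no surgery counts and no amendment date, the actual effect cannot be computed and may be very small. The documents do not support a conclusion that the SAE results are unreliable. The change is a cheap improvement to how they are presented.

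**What to change.** 1. For each SAE that is the major surgery itself, derive a flag giving prescheduled status (yes/no) and timing relative to Amendment 2 (before/after). Complications of surgery are separate events and stay in all tables.
2. Do not define the flag as having met no other seriousness criterion. A planned inpatient operation also meets the hospitalization criterion, so it would escape the flag and remain in the restricted table.
3. Present the treatment-emergent SAE row of the overall summary and the SOC/preferred-term SAE table twice: as reported, and excluding prescheduled major-surgery SAEs from both periods. The second version applies the pre-amendment rule throughout.
4. Add a footnote to both tables stating the two rules, and show the flag in the SAE listing.
5. State in SAP 8.2.1 that the onset-date exception in SAP 8.2 governs the surgery SAE itself, if that is the intention.

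The cost is a review of a small number of surgery cases, one derived flag and two repeated tables. The drawback is that prescheduled status may have to be taken from SAE or surgery records for post-amendment cases.

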3.3. Number of Subjects

3.3.1. Sample Size

As this is an extension study, the sample size was based on the planned sample sizes of studies 998HB102 (N=100) and 9HB02PED (N=20). This might be increased based upon enrollment being greater than expected in these studies.

3.3.2. Study Sample

Subject inclusion and exclusion criteria can be found in Sections 8.1 and 8.2 of the protocol.

3.3.3. Procedures for Discontinuing Treatment and Removal of Subjects from the Study

A subject *must* permanently discontinue rFIXFc for any of the following reasons:

- A Grade 2 or greater allergic drug reaction in association with administration of rFIXFc, as defined below by the Recommendations for Grading of Acute and Sub-Acute Toxic Effects on the World Health Organization WHO scale [[WHO handbook, 1979](#)]:
 - Grade 2 Bronchospasm related to rFIXFc; no parenteral therapy needed
 - Grade 3 Bronchospasm related to rFIXFc; parenteral therapy required
 - Grade 4 Anaphylaxis related to rFIXFc
- A high-titer inhibitor (≥ 5.00 BU/mL)
- Use of FIX products other than rFIXFc, unless it occurs in 1 life-threatening emergency and/or as a result of 1 accidental use, and the Sponsor agrees to retain the subject in the study.
- Any condition a subject develops that precludes him from complying with the study procedures.
- The subject experiences a medical emergency that necessitates discontinuation of treatment.

- Clinical judgment of the Investigator: a subject may have treatment permanently discontinued, if in the opinion of the Investigator, it is not in the subject's best interest to continue with the study treatment.
- The parent or legal guardian can withdraw the subject from the study at will at any time.
- The subject, his parent, and/or legal guardian withdraw consent.
- At the discretion of the Investigator or Sponsor for noncompliance

The reason for discontinuation of study treatment must be recorded in the subject's eCRF.

For any subject who no longer responds to treatment with rFIXFc, as determined by the Investigator, a decision will be made with the Sponsor whether to continue the subject on the study.

Subjects who discontinue treatment should remain in the study to complete protocol-required tests and assessments and then must be permanently withdrawn from the study.

3.3.4. End of Study

The end of study is defined as the last subject's last visit. This will occur once all subjects have completed the study, discontinued prematurely, switched to commercially available rFIXFc when it becomes available in the applicable participating country, or switched to EAP (Expanded Access Program).

3.3.5. Randomization and Blinding

This is an open-label study with no blinding or randomization.

4. ANALYSIS POPULATIONS

For the purpose of this analysis, analysis populations will consist of subjects who enrolled into study 9HB01EXT from parent studies 998HB102 and 9HB02PED.

4.1. All-enrolled Analysis Set

All subjects who consent to participate in 9HB01EXT will be included in the All-enrolled Analysis Set.

4.2. Full Analysis Set (FAS)

Subjects who receive at least 1 dose of rFIXFc in study 9HB01EXT will be included in the Full Analysis Set (FAS). Analyses of efficacy will be performed on the FAS.

4.3. Safety Analysis Set

Subjects who receive at least 1 dose of rFIXFc in study 9HB01EXT will be included in the Safety Analysis Set.

4.4. Surgery Subgroup

Surgery subgroup is defined as subjects who have undergone major surgery or have major surgical/rehabilitation periods described in Section 5.3.3 during study 9HB01EXT.

5. DATA HANDLING

This study is being conducted under the sponsorship of Biogen. Data management is being performed under contract with Quintiles in collaboration with Bioverativ. Statistical analysis is being performed by Biogen, using SAS[®] version 9.3 or higher and, where appropriate, additional validated software. This statistical analysis plan (SAP) is based on protocol Version 4, dated 13 November 2013 and will detail analyses to be performed and summaries to be produced for the final Clinical Study Report (CSR).

5.1. General Principles

The following rules will be followed for all applicable analyses contained in this SAP, unless specified otherwise.

Because the subjects from study 998HB102 and study 9HB02PED are in different age groups (i.e., ≥ 12 years of age for study 998HB102 and < 12 years of age for study 9HB02PED) and may therefore have different safety and efficacy profiles, analyses will be performed separately for subjects from study 998HB102 and for subjects from study 9HB02PED.

For subjects from study 9HB02PED, age cohort (< 6 years old and 6 to < 12 years old) is taken from study 9HB02PED.

Summaries of study 9HB01EXT data will be produced using standard summary statistics. Listings will also only include data from study 9HB01EXT and the treatment regimen associated with each data point, unless specified otherwise. Data collected at unscheduled visits will be included in the definition of the maximum and minimum post-baseline values.

